### **8.3.1.19 Serum calprotectin**

Actual serum calprotectin levels and corresponding change from Part A Baseline values will be summarized by axSpA subpopulation and overall for each visit at which stool samples were taken during Part A using the geometric mean, 95% CI, geometric CV, arithmetic mean, arithmetic SD, median, minimum, and maximum. This analysis will be performed on observed case data only using the OLS.

### **8.3.1.20 Inflammatory Bowel Disease Questionnaire (IBD-Q)**

Summary statistics will be used to summarize each score (Global IBD-Q total score, IBD-Q bowel symptoms score, IBD-Q systemic symptoms score, IBD-Q emotional function score and IBD-Q social function score) using the actual values and change from Part A Baseline values at each visit by axSpA subpopulation and overall. These summaries will be produced for the OLS using observed case data.

Frequency tables by axSpA subpopulation and overall will be produced to show the number and percentage of IBD-Q responders and IBD-Q remitters at each visit. These summaries will be produced for the OLS using observed case data and will be repeated using NRI data.

### **8.3.1.21 Correlation between fecal calprotectin, serum calprotectin, IBD-Q and CRP**

The following correlations will be summarized at Part A Baseline and Week 48 by axSpA subpopulation and overall:

- fecal calprotectin and serum calprotectin
- fecal calprotectin and global IBD-Q total score
- serum calprotectin and global IBD-Q total score
- fecal calprotectin and CRP
- serum calprotectin and CRP
- CRP and global IBD-Q total score

For each considered correlations, number and percentage of subjects with non-missing values and Spearman's rank correlation coefficient along with corresponding 2-sided 95% CI will be reported at each visit. These summaries will be produced for the OLS using observed case data.

### **8.3.1.22 Short-Form 36-Item Health Survey (SF-36)**

Summary statistics of the actual values and change from Part A Baseline values will be used to summarize each SF-36 domain scores and the PCS and MCS scores for each visit by axSpA subpopulation and for all subjects combined. These summaries will be produced for the OLS using observed case data.

Frequency tables will be produced to show the number and percentage of SF-36 PCS and MCS responders for each visit by axSpA subpopulation and for all subjects combined. This summary will be performed on the OLS using observed case data and will be repeated using NRI data.

### **8.3.1.23 Resources utilization**

Summary statistics and frequency distribution (number of subjects by number of medical resources used) will be presented by axSpA subpopulation and all subjects for concomitant medical procedures, health care provider consultations, and in-patient hospitalizations and emergency room visits, including length of stay. These summaries will be produced for the OLS using observed case data.

## **8.3.2 Part B**

The following analyses are not part of the multiplicity-controlled testing procedure described in Section 8.1.1. The p-values reported for these analyses will not be adjusted for multiplicity and will be considered nominal. All efficacy summaries and analyses for Part B will be performed using the RS.

### **8.3.2.1 ASDAS clinical improvement (ASDAS-CII, ASDAS-MI)**

The number and percentage of subjects achieving ASDAS-MI and ASDAS-CII will be summarized in frequency tables by visit and by treatment group. This summary will be produced using observed case data and will be repeated using NRI data. This analysis will be performed using Part A Baseline as reference for the definition of ASDAS-MI and ASDAS-CII.

The statistical analysis of ASDAS-MI and ASDAS-CII at each visit will be based on a logistic regression model which will include factors of treatment group, region, and mNY classification.

The responder rates and adjusted odds ratios with reference to PBO will be estimated from this logistic regression model and presented with 95% 2-sided CIs and p-values. These analyses will be performed using NRI data. These analyses will be performed using Part A Baseline as reference for the definition of ASDAS-MI and ASDAS-CII.

### **8.3.2.2 ASAS20, ASAS40, ASAS5/6, and ASAS PR response**

The number and percentage of subjects achieving each of the ASAS endpoints will be summarized in frequency tables by visit and by treatment group. This summary will be produced using observed case data and will be repeated using NRI data. This analysis will be performed using Part A Baseline as reference for the definition of the ASAS endpoints.

The statistical analysis of ASAS20, ASAS40, ASAS5/6 and ASAS PR at each visit will be based on a logistic regression model which will include factors of treatment group, region, and mNY classification. The responder rates and adjusted odds ratios with reference to PBO will be estimated from this logistic regression model and presented with 95% 2-sided CIs and p-values. These analyses will be performed using NRI data. These analyses will be performed using Part A Baseline as reference for the definition of the ASAS endpoints.

### **8.3.2.3 ASDAS, BASDAI, BASFI and BASMI**

Summary statistics of the actual values, change from Part B Baseline values and change from Part B Baseline values for ASDAS, BASDAI, BASFI and BASMI will be presented by visit and treatment group. These summaries will be produced using observed case data. These summary statistics will be repeated for Part A Baseline.

The changes from Part B Baseline to each visit in Part B for ASDAS, BASDAI, BASFI and BASMI will be compared between treatment groups using a MMRM. The model will include Part B Baseline score as a fixed-effect covariate, treatment group, region, mNY classification, and visit as fixed-effect categorical factors, and Part B Baseline-by-visit and treatment group-by-visit as interaction terms. The multiple visits for each subject will be incorporated as repeated measures (fixed term) within each subject (random term). An unstructured covariance matrix will be used and visit will be treated as a categorical predictor. Summary tables will present the adjusted means for PBO and the CZP doses, the respective differences to PBO, the corresponding p-values, and 95% CIs.

This analysis will be repeated based on change from Part A Baseline with Part A Baseline score as a fixed-effect covariate, treatment group, region, mNY classification, and visit as fixed-effect categorical factors, and Part A Baseline-by-visit and treatment group-by-visit as interaction terms.

### **8.3.2.4 Individual ASAS core components**

Summary statistics will be used to summarize the actual values, change from Part A Baseline values and change from Part B Baseline values by visit for the ASAS score components (note that BASFI is covered in Section 8.3.2.3):

- PtGADA
- Total spinal pain (NRS)
- Average of Questions 5 and 6 of the BASDAI concerning morning stiffness

These summaries will be produced using observed case data.

For each component, the changes from Part B Baseline to each visit in Part B will be compared between treatment groups using a MMRM. (see Section 8.3.2.3). This analysis will be repeated based on change from Part A Baseline.

### **8.3.2.5 Fatigue NRS**

Fatigue (NRS) will be taken from BASDAI Question 1. Summary statistics for actual values, change from Part A Baseline values and change from Part B Baseline values by visit and by treatment group will be used to summarize the fatigue scores at each visit during Part B. This summary will be produced using observed case.

Treatment group comparisons for both CZP groups vs. PBO will be performed based on the change from Part B Baseline to each visit in Fatigue using a MMRM. (see Section 8.3.2.3). This analysis will be repeated based on change from Part A Baseline.

The remaining components of the BASDAI maybe analyzed as well.

### **8.3.2.6 BASDAI50 response**

Frequency tables by visit and by treatment group will be produced to show the number and percentage of BASDAI50 responders at each visit during Part B. This summary will be produced using observed case data and will be repeated using NRI for missing data. This analysis will be performed using Part A Baseline as reference for the definition of BASDAI50.

The statistical analysis of BASDAI50 response at each visit will be based on a logistic regression model which will include factors of treatment group, region, and mNY classification. The responder rates for each treatment group and the adjusted odds ratios with reference to PBO will be estimated from this logistic regression model and presented with 95% 2-sided CIs and p-values. This analysis will be performed using NRI data. This analysis will be performed using Part A Baseline as reference for the definition of BASDAI50.

### **8.3.2.7 ASQoL**

Summary statistics for actual values, change from Part A Baseline values and change from Part B Baseline values by visit and by treatment group will be used to summarize the ASQoL scores at each visit during Part B. This summary will be produced using observed case.

Treatment group comparisons for both CZP groups vs. PBO will be performed based on the change from Part B Baseline to each visit in ASQoL score using MMRM (see Section 8.3.2.3).

This analysis will be repeated based on change from Part A Baseline.

### **8.3.2.8 Work Productivity Survey (WPS)**

Frequency tables will be produced by visit and by treatment group for the answer provided to question 1 of the WPS.

Summary statistics will be used to summarize the actual values, change from Part A Baseline values and change from Part B Baseline values by visit and by treatment group for answers to questions 2 to 9 of WPS. These summaries will be produced using observed case data.

Treatment group comparisons for both CZP groups vs. PBO will be performed for the change from Part B Baseline for answers to questions 2 to 9 using MMRM (see Section 8.3.2.3).

This analysis will be repeated based on the change from Part A Baseline.

### **8.3.2.9 Number of uveitis flares, IBD exacerbations and psoriasis exacerbations**

Separate tables will be produced to summarize incidence of each of these events (uveitis flares, IBD exacerbations and psoriasis exacerbations) during Part B.

These summary tables will display the number and percentage of subjects experiencing the considered event in Part B, number of event, incidence rate, event rate and 100 patient exposure year. Only the events occurring up to Escape Week 0 will be considered. In this style of output, “number of event” will include all occurrences of the event including repeat occurrences in individual subjects, while “number of subjects” will count each subject only once.

The presentation will be performed by treatment group using observed case data.

For each of these events (uveitis flares, IBD exacerbations and psoriasis exacerbations), the summary table will be repeated based on the subset of subjects with a history of occurrence and/or a current occurrence of the event at screening.

### **8.3.2.10 Correlation between fecal calprotectin, serum calprotectin, IBD-Q and CRP**

The following correlations will be summarized at Week 48 and Week 96 by treatment group:

- fecal calprotectin and serum calprotectin
- fecal calprotectin and global IBD-Q total score
- serum calprotectin and global IBD-Q total score
- fecal calprotectin and CRP
- serum calprotectin and CRP
- CRP and global IBD-Q total score

For each considered correlations, number and percentage of subjects with non-missing values and Spearman's rank correlation coefficient along with corresponding 2-sided 95% CI will be reported at each visit. These summaries will be produced using observed case data only.

### **8.3.2.11 Short-Form 36-Item Health Survey (SF-36)**

Summary statistics for actual values, change from Part A Baseline values and change from Part B Baseline values by visit and by treatment group will be used to summarize the SF-36 domain, PCS and MCS scores at each visit during Part B. This summary will be produced using observed case data.

Treatment group comparisons for both CZP groups vs. PBO will be performed based on the change from Part B Baseline in the SF-36 physical function domain, PCS and MCS scores only at the time points of Part B using MMRM (Section 8.3.2.3). This analysis will be repeated based on change from Part A Baseline.

Frequency tables by visit and by treatment group will be produced to show the number and percentage of SF-36 PCS and MCS responders at each visit during Part B. This summary will be produced using observed case data and will be repeated using NRI for missing data. This analysis will be performed using Part A Baseline as reference for the definition of SF-36 PCS and MCS responders.

The statistical analysis of SF-36 PCS and MCS response at each visit will be based on a logistic regression model which will include factors of treatment group, region, and mNY classification. The responder rates for each treatment group and the adjusted odds ratios with reference to PBO will be estimated from this logistic regression model and presented with 95% 2-sided CIs and p-values. This analysis will be performed using NRI data. This analysis will be performed using Part A Baseline as reference for the definition of SF-36 PCS and MCS response.

### 8.3.2.12 Descriptive summaries of other efficacy variables

The below listed efficacy variables will be summarized descriptively by visit and by treatment group as applicable using observed case based on the RS unless otherwise specified.

- ASDAS disease activity (ASDAS-ID, ASDAS-LD, ASDAS-HD and ASDAS-vHD)
- Change from Part A Baseline and change from Part B Baseline in SIJ SPARCC and spine ASspiMRI-a in the Berlin modification scores (summaries based on observed case data only)
- Change from Part A Baseline and change from Part B Baseline in PhGADA
- Change from Part A Baseline and change from Part B Baseline in nocturnal spinal pain (NRS)
- CRP (actual values, change from Part A Baseline values, change from Part B Baseline values, ratio of post-Baseline over Part A Baseline values, ratio of post-Baseline over Part B Baseline values)
- Health status as assessed by the EQ-5D-3L: domains, VAS actual score, change from Part A Baseline and change from Part B Baseline in VAS score
- Change from Part A Baseline and change from Part B Baseline in MASES
- Change from Part A Baseline and change from Part B Baseline in swollen and tender joint counts (44 joint counts). The summaries for TJC will be repeated including only the subjects with a TJC>0 at Part A Baseline or Part B Baseline, as appropriate. Similar approach will be used for SJC.
- Change from Part A Baseline and change from Part B Baseline in spinal mobility as assessed by occiput to wall distance and in spinal mobility as assessed by chest expansion
- Change from Part A Baseline and change from Part B Baseline in fecal calprotectin (summaries based on observed case data only)
- Change from Part A Baseline and change from Part B Baseline in serum calprotectin (summaries based on observed case data only)
- Change from Part A Baseline and change from Part B Baseline in the IBD-Q scores (Global IBD-Q total score, IBD-Q bowel symptoms score, IBD-Q systemic symptoms score, IBD-Q emotional function score and IBD-Q social function score)
- Frequency of IBD-Q responders and IBD-Q remitters (NRI data will be used) using Part A Baseline and Part B Baseline as reference
- Resources utilization: concomitant medical procedures, healthcare provider consultations not foreseen by the protocol, in-patient hospitalizations and emergency room visits

### 8.3.3 Subjects experiencing a flare in Part B

The below listed efficacy variables for subjects experiencing a flare in Part B will be summarized descriptively by visit and randomized treatment group using the FS. If deemed needed, further sensitivity analyses may be conducted excluding subjects incorrectly 'flared'. All summaries will be based on observed case data and will present data as collected at all scheduled study visits following Escape Week 0. Generally, the format of the summaries described here will mirror the format of summaries described in Section 8.3.2.

- ASDAS disease activity (ASDAS-ID, ASDAS-LD, ASDAS-HD, and ASDAS-vHD)
- ASDAS clinical improvement (ASDAS-CII, ASDAS-MI, MI) using Flare Baseline as reference
- ASAS20, ASAS40, ASAS5/6, and ASAS PR using Flare Baseline as reference
- Change from Part B Baseline and change from Flare Baseline in ASDAS, BASDAI and BASMI
- Change Part B Baseline and change from Flare Baseline in SIJ SPARCC and spine ASspiMRI-a in the Berlin modification scores
- Change from Part B Baseline and change from Flare Baseline in all individual ASAS core components:
  - PtGADA
  - Total spinal pain (NRS)
  - BASFI
  - Average of questions 5 and 6 of the BASDAI concerning morning stiffness
- Change from Part B Baseline and change from Flare Baseline in PhGADA
- Change from Part B Baseline and change from Flare Baseline in nocturnal spinal pain (NRS)
- Change from Part B Baseline and change from Flare Baseline in Fatigue (NRS) (from BASDAI). The remaining components of the BASDAI maybe analyzed as well.
- BASDAI50 response using Flare Baseline as reference
- CRP (actual values, change from Part B Baseline values, ratio of post-Baseline over Part B Baseline values, change from Flare Baseline values, ratio of post-Baseline over Flare Baseline values)
- Change from Part B Baseline and change from Flare Baseline in ASQoL
- Change from Part B Baseline and change from Flare Baseline WPS
- Health status as assessed by the EQ-5D-3L: domains, VAS actual score, change from Part B Baseline and change from Flare Baseline in VAS score
- Change from Part B Baseline and change from Flare Baseline in MASES
- Change from Part B Baseline and change from Flare Baseline in spinal mobility as assessed by occiput to wall distance and in spinal mobility as assessed by chest expansion

- Number of uveitis flares, IBD exacerbations and psoriasis exacerbations occurring post ASDAS-defined flare
- Change from Part B Baseline and change from Flare Baseline in fecal calprotectin
- Change from Part B Baseline and change from Flare Baseline in serum calprotectin
- Change from Part B Baseline and change from Flare Baseline in the IBD-Q scores (Global IBD-Q total score, IBD-Q bowel symptoms score, IBD-Q systemic symptoms score, IBD-Q emotional function score and, IBD-Q social function score)
- Frequency of IBD-Q responders and IBD-Q remitters using Part B Baseline and Flare Baseline as reference
- Correlation between fecal calprotectin, serum calprotectin, IBD-Q and CRP
- Change from Part B Baseline and change from Flare Baseline in all SF-36 domains, SF-36 PCS, SF-36 MCS
- Frequency of SF-36 PCS responders and SF-36 MCS responders using Flare Baseline as reference
- Resources utilization: concomitant medical procedures, healthcare provider consultations not foreseen by the protocol, in-patient hospitalizations and emergency room visits

## **9 PHARMACOKINETICS AND PHARMACODYNAMICS**

### **9.1 Pharmacokinetics**

CZP plasma concentrations will be tabulated and summarized using PKSB for each visit at which samples were taken during Part A by axSpA subpopulation using the geometric mean, 95% CI, geometric CV, arithmetic mean, arithmetic SD, median, minimum, and maximum. Plasma concentration time curves of Part A will be plotted for all subjects and Part A treatment-emergent ADAb (Part A TE ADAb) status with titer classification (see Section 9.2).

CZP plasma concentrations will be tabulated and summarized by treatment group using PKSB for each visit of the total study at which samples were taken using the geometric mean, 95% CI, geometric CV, arithmetic mean, arithmetic SD, median, minimum, and maximum. The table will be repeated for TE ADAb status with titer classification (see Section 9.2.).

For each treatment group, plasma concentration time curves of Part B will be plotted and repeated for TE ADAb status with titer classification (see Section 9.2.).

Part B figures will not include post-flare assessments. Separate figures will be produced for subjects experiencing a flare in Part B and start escape therapy including only the post-flare assessments.

Spaghetti plots of CZP plasma concentrations by week from CZP first dosing separated by treatment group and TE ADAb status and titer classification (see Section 9.2.) will be presented for subjects with flare and no flare per NRI approach.

Spaghetti plots of CZP plasma concentrations by week from CZP first dosing separated by treatment group will be presented for flared subjects per NRI by TE ADAb status and titer classification (see Section 9.2.).

Individual plots by subject of CZP Concentrations/ADAb titer and ASDAS score plotted on the Y-axes by visit (X-axis) for the full treatment period, including SFU. Flare data will be displayed on the days relative to Part A.

Concentrations below the limit of quantification (BLQ) will be replaced by the LLOQ divided by 2 for the calculation of descriptive statistics.

Anomalous values will be not included in summaries/analysis and will be reviewed and flagged by pharmacokineticist.

All CZP plasma concentration will be listed at subject-level.

## 9.2 Immunogenicity

Immunogenicity will be assessed through listing of individual results by subject and summary tables. Immunogenicity data will be correlated with PK and efficacy readout.

A cut point will be determined by the bioanalytical laboratory during assay validation. This cut point will be used to determine the status of ADAb in the test sample.

The following definitions will be applied regarding classification of test samples:

- An ADAb status will be confirmed as positive for any sample with an ADAb level that is positive screen and positive immunodepletion.
- An ADAb status of negative will be concluded for any sample with an ADAb level that is either negative screen or positive screen and negative immunodepletion.

Confirmed positive samples will be titrated. The dilution factor will be reported. The titer represents the last dilution factor of the sample's titration series still scoring positive in the screening ADAb assay. ADAb titer dilution factor is presented in the listings and summaries excluding the minimum required dilution, i.e. reportable values are divided by 100.

If the titer for an ADAb level that is positive screen and positive immunodepletion is missing, then a conservative will be used and ADAb status will be consider as positive. No imputation rules apply for the missing titer.

If the ADAb level is positive screen but no confirmatory result could be determined, then then a conservative will be used and ADAb status will be consider as positive.

Anomalous value will be not included in summaries/analysis and will be reviewed and flagged by pharmacokineticist.

Subjects will have the following Baseline ADAb status:

Baseline ADAb Status positive is defined as having an ADAb confirmed positive inhibition result at baseline, Baseline ADAb Status negative is defined as having negative inhibition result at baseline.

Subjects will receive a treatment-emergent ADAb status, inclusive of Baseline and Post-Baseline results (including SFU), and be classified as follows based on the ADAb assay results:

- TE ADAb status positive is defined as either (i) baseline ADAb negative subjects having at least one ADAb confirmed positive sample post baseline or ii) baseline ADAb positive subjects with at least one post baseline sample with  $\geq$ minimum significant ratio (MSR) -fold

increase from baseline on CZP treatment. The MSR will be defined during the process of sample analysis and is disease-specific.

- TE ADAb status negative is defined as having no samples either ADAb positive or with values  $\geq$ MSR -fold increase from baseline.

Once determined positive, the highest titer during Part A and Part B (including Escape and SFU) is used to categorize the subject.

- Positive  $<512$ ,
- Positive  $512- \leq 1024$ ,
- Positive  $>1024$ .

In addition, for some outputs also the subjects with TE ADAb status negative will be presented.

The TE ADAb will be also defined for the different treatment periods. For each Period the SFU visit will be considered:

- Part A TE ADAb status positive is defined as either (i) baseline ADAb negative subjects having at least one ADAb confirmed positive sample post baseline during Part A or ii) baseline ADAb positive subjects with at least one post baseline sample with  $\geq$ MSR increase from baseline on CZP treatment during Part A. Once determined positive, the highest titer during Part A is used to categorize the subject.
- Part A TE ADAb status negative is defined as having no samples either ADAb positive or with values  $\geq$ MSR increase from baseline during Part A.
- Part B TE ADAb Status positive is defined as either (i) baseline ADAb negative subjects having at least one ADAb confirmed positive sample post baseline during Part B or ii) baseline ADAb positive subjects with at least one post baseline sample with  $\geq$ MSR increase from baseline on CZP treatment during Part B. Once determined positive, only the highest titer during Part is used to categorize the subject. For subjects with flare in Part B, any assessments after Escape treatment are not included.
- Part B TE ADAb Status negative is defined as having no samples either ADAb positive or with values  $\geq$ MSR increase from baseline during Part B (excluding any values up to 8 weeks post first Part B dose).
- Escape TE ADAb Status positive is defined as either (i) baseline ADAb negative subjects having at least one ADAb confirmed positive sample post baseline during Escape Part or ii) baseline ADAb positive subjects with at least one post baseline sample with  $\geq$ MSR increase from baseline on CZP treatment during Escape Part B. Once determined positive, only the highest titer during Escape is used to categorize the subject.
- Escape TE ADAb Status negative is defined as having no samples either ADAb positive or with values  $\geq$ MSR increase from baseline during Escape Part. Once determined positive, only the highest titer during Escape is used to categorize the subject.

Summaries will be done using PKSB.

Summary of shift from Baseline ADAb status with titer classification to TE ADAb Status with titer classification by treatment group and for all subjects will be presented during the entire study.

The shift table will be repeated for

- Part A TE ADAb status with titer classification to Part B TE ADAb status with titer classification by treatment group and for all subjects during Part B.
- Part B TE ADAb status with Part B titer classification to Escape Part TE ADAb status with Escape titer classification by treatment group and for all subjects during Escape Part.

The time to achieving TE ADAb for all subjects will be analyzed based on Kaplan-Meier methods. Subjects will be considered to have an event at the time where treatment-emergent ADAb positive is first achieved during treatment period excluding Baseline/pre-treatment. Subjects classified as treatment-emergent ADAb negative will be censored at the time of last available ADAb result. The median and 95% CI based on the Kaplan-Meier estimation will also be presented. A plot of time to first ADAb positivity will be presented.

Number and percentage of subjects with ADAb titer above the specified cut point (“categorized”) at any visit during the treatment period, separated by treatment group will be presented.

A summary of flare responder during Part B (NRI) and ASDAS MI responder at Week 96 (NRI) by treatment group and by highest ADAb titer (“categorized”) per subject will be presented during Part A and Part B (excluding Escape). This table will be repeated for Part B (excluding Escape).

A scatter plot of CZP Plasma Concentration and ADAb titer during Part A for all subjects will be presented. The scatter plot will be repeated for Part B by treatment group.

Spaghetti plots of ADAb titer on a loglog scale by week from CZP first dosing separated by treatment group and TE ADAb status/titer classification will be presented for subjects with flare and no flare per NRI approach.

All individual ADAb results will be listed at subject level.

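### The treatment-emergent ADAb definitions in SAP Section 9.2 do not partition subjects: some fit neither class, and in Part B some fit both

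*SAP*

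**What the plan says.** All of the relevant rules are in SAP Section 9.2.

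- Scope: "Subjects will receive a treatment-emergent ADAb status, inclusive of Baseline and Post-Baseline results (including SFU". Baseline and follow-up samples both enter.
- Sample level: "An ADAb status will be confirmed as positive for any sample with an ADAb level that is positive screen and positive immunodepletion". No titer or fold condition is attached.
- TE positive, limb (i): a baseline-negative subject with a confirmed positive sample afterwards. The Part B form reads "baseline ADAb negative subjects having at least one ADAb confirmed positive sample post baseline during Part B".
- TE positive, limb (ii): "baseline ADAb positive subjects with at least one post baseline sample with" a rise from baseline of at least the MSR while on CZP.
- TE negative: no sample that is ADAb positive and none at or above the MSR-fold rise. The Part A, Part B and Escape versions follow the same pattern within their own period.
- Part B only: "Part B TE ADAb Status negative is defined as having no samples either ADAb positive or with values" at or above the MSR-fold rise "during Part B (excluding any values up to 8 weeks post first Part B dose". The only samples that the Part B positive definition sets aside are those after escape treatment.
- Kaplan-Meier analysis of time to TE ADAb: the event is first becoming TE positive, and "Subjects classified as treatment-emergent ADAb negative will be censored at the time of last available ADAb result". No other censoring rule is given.

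**The concern.** A status that every subject is meant to receive should put each subject in exactly one class. These definitions fail in two ways.

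First, positive and negative are not complements for baseline-positive subjects. Positive asks for a fold rise, but negative asks for no positive sample at all. The ground between the two has no name.

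Second, the 8-week window in Part B is attached to one definition and not the other, so the two are judged on different sets of samples.

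TE status with titer class is the row or column variable in the shift tables (baseline to TE, Part A to Part B, Part B to Escape). It also stratifies the PK tables and plots in Section 9.1 and decides who is an event or censored in the Kaplan-Meier analysis. Two programmers who follow the text faithfully could produce different tables.

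**Working it through.** No figure in the plan needs reproducing; the check is logical. Each sample is coded N (negative), P (positive, below the MSR-fold rise) or M (positive, at or above it). For a baseline-negative subject only N and P matter. Baseline means the baseline ADAb status defined in Section 9.2, and the on-CZP condition in limb (ii) is taken as met.

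**Overall status, two post-baseline samples**

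- Baseline negative: 2 × 2 = 4 patterns. Each falls in exactly one class.
- Baseline positive: 3 × 3 = 9 patterns. The 9 − 4 = 5 that contain an M are TE positive only.
- Of the other 4, (P,P), (P,N) and (N,P) are not positive, because there is no MSR-fold rise, and not negative, because a sample is ADAb positive. They are in neither class.
- (N,N) is negative if only post-baseline samples count. If the baseline sample counts, as the scope sentence suggests, it is also in neither class, and then every baseline-positive subject without an MSR-fold rise is unclassified overall.

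**Part B, one sample up to 8 weeks after the first Part B dose and one later**

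| Baseline | Early, late | Meets positive | Meets negative | Result |
|---|---|---|---|---|
| Negative | N, N | no | yes | one |
| Negative | N, P | yes | no | one |
| Negative | P, N | yes | yes | **both** |
| Negative | P, P | yes | no | one |
| Positive | N, N | no | yes | one |
| Positive | P, N | no | yes | one |
| Positive | N, P | no | no | **neither** |
| Positive | P, P | no | no | **neither** |
| Positive | M, N | yes | yes | **both** |
| Positive | N, M; P, M; M, P; M, M | yes | no | one |

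Of 4 + 9 = 13 patterns, 2 are in both classes, 2 in neither and 9 in one. These are counts of patterns, not of subjects. Part A and Escape have the gap but not the overlap, because neither has a window.

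**Size.** The SAP gives neither baseline positivity nor the ADAb sampling times, which Section 2.2.2.4 leaves to the protocol. Purely as an illustration, an assumed 2% to 10% baseline positivity among the 210 planned for Part B gives 0.02 × 210 = 4.2 to 0.10 × 210 = 21 baseline-positive subjects. That is a ceiling for the overall gap, because any who reach the MSR-fold rise are TE positive.

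**The case against.** The best defence is that the intent can be guessed: negative means not positive, and the 8-week window was meant for both Part B definitions. That may well be so. But Section 9.2 writes out negative as its own condition, attaches the window to one definition, and states no residual class or order of precedence. A guess is not a specification.

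Four stronger readings are tempting and not supported.

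- A reader might infer that subjects with a negative screen at baseline get no baseline status, because "Baseline ADAb Status negative is defined as having negative inhibition result at baseline". The rule for any sample in the same section already calls a negative screen ADAb negative, and a baseline sample is a sample. This is loose wording.
- A reader might infer that a subject first positive at the Safety Follow-Up (SFU) visit is neither event nor censored. Section 9.2 says SFU is considered for each period, Section 9.1 speaks of the treatment period as including SFU, and the Kaplan-Meier text excludes only baseline and pre-treatment results. Section 3.3.2 ends the treatment period earlier, so the term is unclear, but no more than that.
- A reader might infer that every baseline-positive subject without a rise is unclassified in every period. The period definitions look only at samples in that period, so a subject whose samples there are all negative is classed negative.
- A reader might infer that the early Part B positives are antibody carried over from Part A. The SAP does not say why the window exists.

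On consequences, part of the objection stands. The columns of the TEAE table in Section 10.2 turn on reaching a titer of 1024, and the flare and ASDAS-MI summary by antibody uses highest titer, so neither depends on the gap. All individual results are listed, so no data are lost.

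**Conclusion.** The point holds for two defects.

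(a) A baseline-positive subject with no MSR-fold rise but at least one post-baseline positive sample has no overall TE class. The same holds within Part A or Escape when such a sample falls in that period, and within Part B when it falls after the 8-week window.

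(b) In Part B, a subject whose only qualifying sample lies inside the window, and whose later samples are negative, is TE positive and TE negative at once.

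Subjects in (a) have no cell in the shift tables and TE-status PK outputs, and are neither event nor censored in an analysis stated to be for all subjects. Subjects in (b) have two cells in outputs that use Part B status. Defect (b) needs ADAb samples inside the window. The schedule is not shown, but the exclusion clause presupposes such values.

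The number of subjects is unknown. The affected outputs are descriptive, and the primary flare comparison does not use TE status. It should be corrected because the rules are wrong as written, but it does not threaten the trial's main conclusion.

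**What to change.** In Section 9.2:

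1. Define TE negative, overall and for Part A, Part B and Escape, as not TE positive. State that this includes baseline-positive subjects without an MSR-fold rise.
2. Apply the exclusion of values up to 8 weeks after the first Part B dose identically to the Part B positive and negative definitions.

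With both changes, each of the 13 Part B patterns above has exactly one class, and so does every overall pattern. The plan should also say how a subject with no evaluable Part B sample after the window is shown, so that absence of data is not read as negative.

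The cost is SAP wording and derivation code; no new samples are needed. Subjects who meet the positive criterion only in the first 8 weeks of Part B become Part B TE negative. In the table these are patterns (P,N) for baseline-negative subjects and (M,N) and (M,P) for baseline-positive subjects. Baseline-positive subjects now without a class join the negative group.
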